6.5.1 Adverse Events (AEs)

AEs will be summarized by MedDRA system organ class (SOC) and preferred term (PT) in descending order unless otherwise specified. For the summary of number of subjects, if a subject reports more than one AE that was coded to the same SOC or PT, the subject will be counted only once for that specific system organ class or preferred term. For the summary of number of AEs, all AEs will be counted.

The number and percentage of subjects experiencing TEAEs will be tabulated by treatment according to the following categories:

- Overall summary of TEAEs.
- TEAEs by system organ class and preferred term.
- TEAEs by system organ class, preferred term and maximum severity.
- TEAEs by system organ class, preferred term and causality.
- TEAEs by preferred term (in order of descending frequency in the total JTE-451 group).
- TEAEs leading to study discontinuation by system organ class and preferred term.
- Serious AEs (SAEs) by system organ class and preferred term.

- SAEs leading to study discontinuation by system organ class and preferred term.

In addition, adverse drug reactions (ADRs) will be summarized. Per ICH E2A guidance, all noxious and unintended responses to a medicinal product related to any dose should be considered ADRs. The phrase “responses to a medicinal product” means that a causal relationship between a medicinal product and an AE is at least a reasonable possibility, i.e., the relationship cannot be ruled out. For the purpose of analysis, all TEAEs that are related, possibly related or has missing relationship to the study drug will be considered as ADRs. The following summaries of ADRs will be presented:

- Number of ADRs by system organ class, preferred term and maximum severity.
- Number of subjects with ADRs by preferred term (in order of descending frequency in the total JTE-451 group)

Listings will be provided for AEs, SAEs and AEs leading to study discontinuation.

6.5.2 Medical History

Subjects with significant medical history conditions and/or surgeries, the corresponding system organ class and preferred term coded from the MedDRA (Version 23.0) will be presented in the data listing.

6.5.3 Prior and Concomitant Medications

Prior medications and concomitant medications will be listed in the data listings. Concomitant medications will be summarized by ATC Level 3 term, drug preferred term and treatment group.

6.5.4 Clinical Laboratory Tests

Descriptive statistics of observed results and change from baseline for hematology, serum biochemistry, coagulation and continuous urinalysis will be presented by time point and treatment group. Frequency and percentage of the distribution of discrete urinalysis tests will be presented by time point. Number and percentage of subjects with treatment-emergent PCS abnormal values will be summarized by treatment group.

The number and percentage of subjects with post-baseline abnormalities in liver tests will be summarized by treatment group according to [Table 3](#).

Table 3. Criteria for Categorical Analysis in Liver Tests

Parameter	Specified Value			
ALT	ALT \geq ULN \times 3	ALT \geq ULN \times 5	ALT \geq ULN \times 10	ALT \geq ULN \times 20
AST	AST \geq ULN \times 3	AST \geq ULN \times 5	AST \geq ULN \times 10	AST \geq ULN \times 20
ALT and AST	ALT and AST \geq ULN \times 3	ALT and AST \geq ULN \times 5	ALT and AST \geq ULN \times 10	ALT and AST \geq ULN \times 20
ALT or AST	ALT or AST \geq ULN \times 3	ALT or AST \geq ULN \times 5	ALT or AST \geq ULN \times 10	ALT or AST \geq ULN \times 20
T-Bil	T-Bil $>$ ULN \times 1.5		T-Bil $>$ ULN \times 2	
ALP	ALP $>$ ULN \times 1.5			
ALT and T-Bil	ALT \geq ULN \times 3 and T-Bil \geq ULN \times 1.5		ALT \geq ULN \times 3 and T-Bil \geq ULN \times 2	
AST and T-Bil	AST \geq ULN \times 3 and T-Bil \geq ULN \times 1.5		AST \geq ULN \times 3 and T-Bil \geq ULN \times 2	
ALT, AST, ALP and T-Bil	ALT \geq ULN \times 3, AST \geq ULN \times 3, ALP \geq ULN \times 2 and T-Bil \geq ULN \times 2			
ALT and AST	ALT or AST $>$ ULN \times 3 at any treatment visit and any of the following AEs: Nausea, Vomiting, Anorexia, Abdominal pain or Fatigue, reported within +/- 14 days of the abnormal AT values.			

Other clinical laboratory tests (e.g., drug abuse, alcohol screen, viral serology, pregnancy) will be listed in the data listings.

Qualitative urine parameters are generally reported by a descriptive score, which may differ between laboratories. For pooling the data, the qualitative results will be mapped to a four-point scale. A clinical review will be performed on the mapping of the descriptive scores to the four-point scale; and the descriptive scores will be remapped where appropriate. The four-point scale will be used in the determination of the PCS abnormalities.

The mean profile may be presented for selected laboratory parameters.

6.5.5 Vital Signs

Descriptive statistics of observed results and change from baseline for vital signs and body weight will be presented by time point and treatment group. Number and percentage of subjects with treatment-emergent PCS abnormal values will be presented by treatment group.

6.5.6 12-Lead ECG

Descriptive statistics of observed results and change from baseline will be presented by time point and treatment group for RR, PR, QRS, QT and QTcF intervals. The number and percentage of subjects with treatment-emergent PCS abnormal values will be presented by treatment group. Clinical interpretation of overall ECG findings will be summarized by time point and treatment group.

6.5.7 Study Medication Exposure and Compliance

A summary of total duration of study medication exposure, which is calculated as (last dose date of study drug – first dose date of study drug + 1), will be presented by treatment group. Average daily dose will also be summarized by treatment group, which is calculated as (total dose of study drug taken/total duration of study medication exposure), where the total dose is calculated as [(total number of tablets/4) \times daily dose level in the treatment group (0, 400 mg or 800 mg)].

Study drug compliance will be summarized between visits and overall for each treatment group. Study drug compliance will also be presented as categories <80%, 80%-120% and >120%.

6.6 Pharmacokinetic Analysis

[figure not shown]
All PK data will be summarized or analyzed based on the PK population.

6.6.1 Method of PK Data Representation

The PK data including individual data and descriptive statistics for plasma drug concentrations will be represented with 3 significant values except for CV% which will be represented to 1 decimal place. The ratio values (see Section 6.6.2) will be displayed to 2 decimal places.

[figure not shown]
6.6.2 Descriptive Statistics of Plasma Concentrations

Descriptive statistics of plasma concentration data for JTE-451 will be presented by treatment and visit (nominal time point) with n, arithmetic mean, geometric mean, SD, CV%, median, minimum and maximum. The mean ratio of trough concentration relative to the lowest dose will be calculated. Mean plasma concentration-time profiles will be plotted by treatment on linear scales. Below the limit of quantification (BLQ) concentrations will be treated as zero for descriptive statistics.

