1.3.2 Justification for Study Design

A parallel group, placebo-controlled design will be employed in this study to evaluate the effect of JTE-451 on the efficacy and safety of JTE-451 compared to placebo in subjects with plaque psoriasis. Briefly, upon completion of all protocol-mandated screening procedures, qualified subjects will be randomized at Visit 2 in a 1:1:1 ratio to one of the following three parallel dose groups: JTE-451 200 mg BID (400 mg/day), JTE-451 400 mg BID (800 mg/day) or placebo BID (approximately 50 subjects to be randomized per group) and will receive the double-blind treatment for 16 weeks followed by a 4-week Follow-up Period. To minimize potential confounders in efficacy responses, randomization will be stratified based on prior exposure to biologic therapy (i.e., biologic-naïve vs. biologic-experienced subjects) and body weight (i.e., <90 kg vs. ≥90 kg at Visit 2). No clinically meaningful food effect on the PK of JTE-451 was shown in the single ascending dose study [REDACTED] thus, study drug will be administered regardless of meals. Based on the PK characteristics of the compound, the protocol requires the study drug administration twice a day, at approximately 12-hour intervals. The duration of the double-blind treatment period is sufficient to obtain the proof-of-efficacy for JTE-451 in subjects with plaque psoriasis. The duration of the Follow-up Period is set to approximately 4 weeks; standard duration for similar outpatient studies administered an

investigational product. Based on the PK characteristics of JTE-451, this period is considered conservative, as JTE-451 clears the human body within approximately one day after the last dose.

[figure not shown]
The efficacy parameters assessed in this study are consistent with the standards in the industry in similar psoriasis trials (e.g., PASI, sPGA, BSA).

[REDACTED] To minimize the chances of errors, all calculations of derived parameters will be done by the Sponsor based on the appropriate core data points collected and documented by the Investigators.

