3.8.6.1 Trough Concentration

Trough (pre-dose) plasma concentrations of JTE-451 at Weeks 2, 4, 8 and 12 will be summarized in terms of the number of subjects, arithmetic mean, standard deviation, coefficient of variation (CV%), median, minimum and maximum by treatment and visit. The relationship between the dose and trough plasma concentrations of JTE-451 will also be assessed.

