4.4 Pharmacokinetic (PK) Population

The PK population consists of the randomized subjects who receive at least one dose of JTE-451 and have at least one usable JTE-451 plasma concentration measurement.

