6.1 Sample Size

Approximately 150 eligible subjects (50 subjects in each treatment group) will be randomized into the double-blind treatment period.

The sample size estimation is based on the primary efficacy parameter of the proportion of subjects achieving PASI-75 at EOT.

Taking into consideration a 15-20% treatment discontinuation rate, about 50 subjects per group will be randomized into the double-blind treatment period.

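### SAP 6.6.2 sets BLQ concentrations to zero and also asks for a geometric mean, so one BLQ value in a treatment-by-visit cell makes that geometric mean zero or undefined

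*SAP*

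**What the plan says.** SAP 6.6.2 summarises JTE-451 plasma concentrations by treatment and visit "with n, arithmetic mean, geometric mean, SD, CV%, median, minimum and maximum". It then adds "The mean ratio of trough concentration relative to the lowest dose will be calculated" without saying which mean is meant. The paragraph closes with the rule "Below the limit of quantification (BLQ) concentrations will be treated as zero for descriptive statistics". No statistic is exempted.

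No other visible section changes this. SAP 6 (general methodology) adds only CV% for plasma concentrations. SAP 6.6.1 covers display precision. SAP 4.4 admits any subject dosed with JTE-451 who "have at least one usable JTE-451 plasma concentration measurement" and has no rule that removes BLQ values. Protocol 3.8.6.1 lists "arithmetic mean, standard deviation, coefficient of variation (CV%), median, minimum and maximum by treatment and visit" for troughs, with no geometric mean. The SAP therefore added the geometric mean, and its BLQ rule does not provide for it.

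**The concern.** Zero substitution is workable for an arithmetic mean or a median, but not for a geometric mean. A plan that applies it to all descriptive statistics fixes the result in any affected cell at an uninformative value, or leaves the outcome to how the program handles the logarithm of zero. If zeros become missing on the log scale, the geometric mean rests on fewer subjects than the n printed beside it.

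BLQ troughs are plausible. Protocol 1.3.2 states that "JTE-451 clears the human body within approximately one day after the last dose", and subjects dose themselves at home between visits. Subjects who stop early are asked to complete the Visit 7 procedures, which include PK sampling, as soon as possible after the last dose (Protocol 3.4 and Table 1). Whether those samples join the Week 16 summary is not stated.

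What is at stake is the readability of one descriptive PK statistic under a secondary objective, and of the trough ratio if that ratio is built on geometric means.

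**Working it through.** The plan states no figure to reproduce; the check concerns a definition.

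**Inputs.** The SAP 6.6.2 rules above. Cell size: about 50 per group randomised (SAP 6.1: "Taking into consideration a 15-20% treatment discontinuation rate, about 50 subjects per group will be randomized"). After discontinuation, 50 × 0.80 = 40 to 50 × 0.85 = 42.5 remain, so cells of 40 to 50 are considered. The BLQ rate and LLOQ are not in the documents. I assume 0.5% to 5% per sample, and LLOQ = 1 on a scale where the typical trough is 100.

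**Step 1: the definition.** Product form: GM = (x₁ × x₂ × … × xₙ)^(1/n). With one xᵢ = 0 the product is 0, so GM = 0 whatever the other values are. Log form: GM = exp[(Σ ln xᵢ)/n]. With one xᵢ = 0, ln xᵢ = −∞ and the mean log is undefined (0 only as a limit).

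**Step 2: size in an illustrative cell.** Log-normal sample, n = 50, true geometric mean 100, log-SD 0.8, one arbitrary value set to BLQ:

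| Handling of the BLQ value | Geometric mean |
|---|---|
| No BLQ value | 96.3 |
| BLQ = 0, as written | 0 |
| BLQ left out (49 values) | 98.1 |
| BLQ = LLOQ/2 = 0.5 | 88.3 |

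The arithmetic mean moves only from 130.2 to 129.4, and the median stays at 100.5. The implied value replaced is about (130.2 − 129.4) × 50 = 40 from rounded means (38.4 unrounded). This is below the geometric mean, so leaving it out raises the result.

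That direction is not general. In a second sample with n = 40 the arithmetic mean fell from 130.33 to 127.03, so the value replaced was about 3.30 × 40 = 132. This is above the geometric mean, and leaving it out lowered the result from 100.2 to 99.5.

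**Step 3: chance that a cell is affected.** P(at least one BLQ) = 1 − (1 − p)ⁿ, with samples from different subjects taken as independent:

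| Assumed BLQ rate p | n = 40 | n = 50 |
|---|---|---|
| 0.5% | 1 − 0.995⁴⁰ = 18% | 22% |
| 1% | 33% | 40% |
| 2% | 55% | 64% |
| 5% | 1 − 0.95⁴⁰ = 87% | 92% |

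**Step 4: the trough ratio.** The lowest dose is 200 mg BID. If the ratio uses geometric means, a BLQ value in a 200 mg cell puts 0 in the denominator and the ratio is undefined. A BLQ value only in the matching 400 mg cell makes the ratio 0. If it uses arithmetic means, it stays computable.

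**The case against.** The best defence is that little depends on this statistic. The trough statistics promised in Protocol 3.8.6.1 can all be computed under zero substitution, and no hypothesis test, decision rule or efficacy analysis uses the geometric mean. In product form a geometric mean of 0 is defined, and printed beside a minimum of 0 a reader would see the cause. Silent dropping of zeros is a guess about programming. The BLQ rate may be very low. All of this stands, and it limits the severity. It does not make a geometric mean of 0 a usable summary of a cell in which nearly every value is positive.

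Several stronger readings are tempting, and the documents do not support them:

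- A reader might infer that trough level is the only PK parameter in view. Protocol 3.8.6.3 also names apparent clearance and volume from a population analysis (SAP 6.6.4 says such analyses may be performed), and the BLQ rule is confined to descriptive statistics.
- A reader might infer that the dose groups can no longer be compared. They can, on the arithmetic mean and median.
- A reader might infer that dropping zeros must inflate the geometric mean. In step 2 it moved by about 2% up in one sample and under 1% down in the other, depending on the value replaced.
- A reader might infer that one missed dose gives a BLQ trough. Clearance within about one day does not establish this without a half-life or an LLOQ.
- A reader might infer a pre-first-dose cell in which every value is BLQ. Figure 2 is not shown, so whether such a sample is taken cannot be confirmed.

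**Conclusion.** Wrong as written, minor severity. Following SAP 6.6.2 literally gives a geometric mean of 0 or an undefined one in every treatment-by-visit cell with at least one BLQ value. A program that drops zeros gives one on fewer subjects than the n shown. This part is arithmetic and rests on no assumption.

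The effect is confined to that statistic and, if it is built on geometric means, the trough ratio. The arithmetic mean, SD, CV%, median, minimum and maximum remain computable. The 18% to 92% chance per cell depends entirely on the assumed BLQ rate of 0.5% to 5% and on independence between subjects. The documents support no narrower range.

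**What to change.** In SAP 6.6.2:

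1. Limit BLQ = 0 to the statistics other than the geometric mean.
2. For the geometric mean, name one convention in advance and apply it to all samples taken after the first dose, including pre-dose troughs. Leaving out BLQ values and showing the n used is acceptable, and so is substituting LLOQ/2. Step 2 gives 98.1 and 88.3 for the two, so the choice should be made before the data are seen. The scope needs stating because Protocol 3.8.6.1 treats trough and pre-dose as the same thing, and the Figure 2 notes separate those samples from post-dose ones. A rule worded for post-dose samples alone could leave BLQ troughs at zero.
3. Report the number of BLQ values in each cell.
4. State which mean the trough ratio to the lowest dose uses.

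The cost is a few sentences in the SAP and one extra column in the table, with no new data. What remains is a small dependence of the geometric mean on the chosen convention, which the BLQ count makes visible.

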6.6.4 Population Pharmacokinetic Analysis

Population PK (PPK) analyses may be performed. Population PK analysis plan will be specified in a separate analysis document and the results of PPK analyses will be presented in a standalone report separately from the Clinical Study Report.

7. SUBJECT DATA LISTING

Subject listings of all the data collected in the study database, including eCRF data and any external data transfers (such as clinical laboratory results), will be presented by treatment group and subject number.

If a subject prematurely discontinues the study, additional subjects may be enrolled at the discretion of the Sponsor, as appropriate.

8. SOFTWARE AND QUALITY CONTROL

All analysis will be performed using SAS® Version 9.4 or higher. The SOPs of [REDACTED] will be followed in the creation and quality control of all tables, listings and analysis.

9. REFERENCES

Please see the [references](#) in protocol.

10. APPENDICES

10.1 General Clinically-Significant Criteria for Safety Parameters

Parameter (Full Names)	Reporting Unit	Clinically Significant Criteria ¹	
		Low	High
Hematology			
Hematocrit	%	Male ≤37% Female ≤32%	NA
Hemoglobin	g/dl	Male ≤11.5 Female ≤9.5	NA
White blood cell	E3/mm ³	≤2.8	≥16.0
Platelets	E3/mm ³	≤75	≥700
Mean corpuscular hemoglobin	pg/cell	--	--
Mean corpuscular hemoglobin concentration	g/dl	--	--
Mean corpuscular volume	fL	--	--
Red blood cell	E6/mm ³	≤3.5	NA
Differential			
Bands or (Band neutrophil (stab))	%	NA	≥10%
Basophil (absolute)	E3/mm ³	NA	≥0.4
Basophil (%)	%	NA	≥5%
Lymphocytes (absolute)	E3/mm ³	≤0.5	≥4.5
Lymphocytes (%)	%	≤10%	≥80%
Monocytes (absolute)	E3/mm ³	NA	≥1.5
Monocytes (%)	%	NA	≥ 20%
Neutrophils (absolute)	E3/mm ³	≤1.0	
Neutrophils (%)	%	≤15%	≥90%
Eosinophils (absolute)	E3/mm ³	NA	≥0.7
Eosinophils (%)	%	NA	≥10%
Coagulation			
Prothrombin time	seconds	NA	≥16
International Normalized Ratio	ratio	NA	≥2.00
Partial thromboplastin time	Seconds	NA	≥50

¹ Can be revised as appropriate, but should be consistent within the project.

Parameter (Full Names)	Reporting Unit	Clinically Significant Criteria ¹	
		Low	High
Heart Function			
Aspartate transaminase	IU/l	NA	≥3 x UNL
Lactic dehydrogenase	U/L	NA	≥3 x UNL
CPK (MB Fraction)	µg/L	--	--
Liver Function			
Alkaline Phosphatase	IU/l	NA	≥3 x UNL
Alanine transaminase	IU/l	NA	≥3 x UNL
Total Bilirubin	mg/dl	NA	≥2.0
Gamma-glutamyltransferase	IU/l	NA	≥3 x UNL
Total Protein	g/dl	≤4.5	≥9.0
Albumin	g/dl	≤2.5	≥6.5
Renal Function			
Blood urea nitrogen	mg/dl	NA	≥30
Creatinine	mg/dl	NA	≥2.0
Thyroid Function			
T ₃ Uptake, total	nmol/L	--	--
Reverse T ₃	nmol/L	--	--
Thyroxine (T ₄)	nmol/L	--	--
Human chorioic gonadotropin	IU/L	--	--
Free T ₄	pmol/L	--	--
Thyroid- stimulating hormone	mU/L	--	--
Follicle- stimulating hormone	--	--	--
Lipid Chemistry			
Total cholesterol	mg/dl	NA	≥300
LDL cholesterol	mg/dl	--	--
HDL cholesterol	mg/dl	--	--
Ratio (LDL/HDL)	Fraction	--	--
Triglycerides	mg/dl	NA	≥300

Parameter (Full Names)	Reporting Unit	Clinically Significant Criteria ¹	
		Low	High
Electrolytes			
Chloride	MEq/l	≤90	≥112
Potassium	MEq/l	≤3.0	≥5.8
Sodium	MEq/l	≤130	≥150
Bicarbonate	MEq/L	--	--
Metabolic			
Calcium	mg/dl	≤7.0	≥15.5
Phosphate	mg/dl	≤1.5	≥6.0
Blood Glucose	mg/dl	≤50 (fasting)	≥180 (fasting)
Uric Acid	mg/dl	NA	Male ≥10.5 Female ≥8.5
Cancer			
Prostate-specific antigen	--	--	--
Alpha-fetoprotein	--	--	--
Viral tests			
HIV	--	--	--
HIV ₂	--	--	--
Hepatitis A virus	--	--	--
Hepatitis A antibody	--	--	--
Hepatitis B virus	--	--	--
Hepatitis B surface Antigen	--	--	--
Hepatitis B core antigen	--	--	--
Hepatitis C virus	--	--	--
Urinalysis			
(Urine) protein		NA	Increase≥2
(Urine) glucose		NA	Increase≥2
(Urine) bilirubin		NA	Increase≥2
Occult blood		NA	Increase≥2
Color		NA	Increase≥2
Ketone		NA	Increase≥2
Leukocyte esterase		NA	Increase≥2
pH		Decrease≥2	Increase≥2
Turbidity		NA	Increase≥2
Urobilinogen		NA	Increase≥2
Specific gravity		≤1.005	NA

¹ Can be revised as appropriate, but should be consistent within the project.

Parameter (Full Names)	Reporting Unit	Clinically Significant Criteria ¹	
		Low	High
Vital Sign			
Systolic blood pressure	mmHg	≤90 and ≥20 decrease	≥180 and ≥20 increase
Diastolic blood pressure	mmHg	≤50 and ≥15 decrease	≥105 and ≥15 increase
Pulse rate	bpm	≤50 and ≥15 decrease	≥120 and ≥15 increase
Body Temperature	C°	NA	≥1.11 C° Increase
Respiration rate	#/min	≤ 10	--
Height	cm	--	--
Weight	kg	≥7% decrease	≥7% increase
Body mass index	kg/m ²		
Hip Circumference	cm		
Waist Circumference	cm		
ECG			
Heart rate	bpm	<50	>100
R-R interval	msec	--	--
PR interval	msec	NA	>200 msec and >Baseline
QRS interval	msec	NA	>120 msec and >Baseline
QT interval	msec	NA	>450 and >30 increase
QTc interval	msec	<=350 and Baseline<375	>450 or >480 or >500 with Baseline <450
QTc interval ¹	msec	NA	>30 increase or >60 increase

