3.5 Study Procedures

[figure not shown]

Figure 1. Study Schema

Table 1. Schedule of Study Procedures

	Screening Period	Treatment Period							Follow-up Period
Duration/ Study Week (Day) ^a	Up to 4 weeks	Week 0 (Day 1)	Week 2 (Day 14±2)	Week 4 (Day 28±2)	Week 8 (Day 56±4)	Week 12 (Day 84±4)	Week 16 (Day 112±4)	Week 20 (Day 140±4)	
Visit	1	2	3	4	5	6	7	8	
Informed Consent ^b	X								
Inclusion/ Exclusion Criteria	X	X							
Medical History	X	X							
Demographic Information	X								
Review Prior/ Concomitant Medications	X	X	X	X	X	X	X	X	
Physical Exam	X	X	X	X	X	X	X	X	
Vital Signs including Weight	X	X	X	X	X	X	X	X	
Height and Calculate BMI	X								
12-Lead ECG	X	X		X				X	
Chest Radiography ^c	X								
Quantiferon-TB Gold Plus Test	X								
Drugs of Abuse Screen	X								
Viral Serology	X								
FSH ^d	X								
Pregnancy Test ^d	X	X	X	X	X	X	X	X	
HbA1c	X								
Serum Biochemistry	X	X	X	X	X	X	X	X	
Hematology	X	X	X	X	X	X	X	X	
Urinalysis	X	X	X	X	X	X	X	X	
Coagulation	X	X	X	X	X	X	X	X	
Psoriasis Body Surface Area	X	X	X	X	X	X	X	X	
PASI	X	X	X	X	X	X	X	X	
sPGA	X	X	X	X	X	X	X	X	
Skindex 16	X	X	X	X	X	X	X	X	
Itch NRS ^e									
Digital Photography ^f		X					X		
Randomization using IWRS		X							
Access IWRS and Dispense Study Drug ^g		X	X	X	X	X			
Collect Study Drug and Check Compliance ^j			X	X	X	X	X		
Study Drug Administration ^k		X	X	X	X	X			
JTE-451 PK Blood Samples ^l		X		X	X	X	X		
Document Adverse Events ^m	X	X	X	X	X	X	X	X	

Note: All study procedures should be performed at each study visit prior to study drug administration; except for appropriate PK sample collection procedures as discussed below (see [Figure 2](#)). When scheduled at the same time points, ECG and vital sign parameters collection activities should be performed prior to (or at least 15 minutes after) procedures involving venipuncture [REDACTED]

- a. The target day for each visit after randomization will be calculated relative to the date of Visit 2. Every attempt should be made to have the subject attend each visit within the windows specified in the table. The study site is encouraged to make a reminder phone call to the subject before the scheduled visit. However, if a subject is unable to attend a visit within the specified windows, the visit should be scheduled as closely as possible to these windows. A subject should not skip a protocol-specified visit due to scheduling difficulties.

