3.5.6.14 Serum Biochemistry

Blood samples to assess ALP, albumin, ALT, AST, bilirubin, blood urea nitrogen, calcium, carbon dioxide, chloride, creatinine phosphokinase, creatinine, gamma-glutamyl transferase, globulin, glucose, C-reactive protein, lactate dehydrogenase, low-density lipoprotein cholesterol, phosphate, potassium, protein, sodium, total cholesterol, triglyceride, urate will be obtained under fasted conditions according to the schedule summarized in [Table 1](#).

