Inpatient Hospitalization/Prolongation of Hospitalization: Any admission (even if less than 24 hours) to a healthcare facility. Admission also includes transfer within the hospital to an acute/intensive care unit (e.g., medical floor to the coronary care unit). Initial and prolonged hospitalizations that **do not** meet this SAE criterion include those due to social and/or convenience reasons (e.g., lack of personal care at home, unable to transfer to non-acute facility), admission to rehabilitation/hospice/skilled nursing facilities, emergency room visits,

same-day/outpatient/ambulatory procedures, and those for pre-planned, elective procedures for a pre-existing condition that did not worsen after the informed consent has been signed (no AE present). However, if the hospitalization was prolonged due to a complication of a pre-existing condition, the complication (same diagnosis) would qualify as an SAE.

Disability: A substantial disruption of a person's ability to conduct normal life functions.

Life-threatening: Any AE that places the patient or subject, in the view of the Investigator, at immediate risk of death, i.e., it does not include an event that had it occurred in a more severe form, might have caused death.

Physical Examination, Vital Signs, Laboratory Test and ECG Abnormalities: Any abnormalities fulfilling the criteria for an SAE should be reported as such, in addition to being recorded as an AE in the CRF. Any abnormal vital sign, physical finding or laboratory/ECG result which is clinically-significant (i.e., meets one or more of the following conditions) should be recorded as a single diagnosis on the AE page in the CRF:

- Accompanied by clinical symptoms
- Leads to permanent discontinuation of study drug
- Requires a change in concomitant therapy (e.g., addition of, interruption of, discontinuation of, or any other change in a concomitant medication, therapy or treatment).

This does not apply to abnormal vital signs, physical finding or laboratory/ECG results that do not meet the clinical-significance criteria or parameters that are a result of an AE, which has already been reported.

Pre-existing conditions detected at the Screening Visit (Visit 1), including abnormalities in ECG, physical examination, vital signs and laboratory tests, are considered to be medical history.

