Appendix 1. Permitted Medications to be used with Caution

Use of the following medications are permitted during the study; however, caution should be used when the medications [REDACTED] are co-administered with JTE-451. Please refer to Section 3.5.5.1.3 for detail of cautions.

Strong CYP3A4 inhibitor				
Diltiazem	--	--	--	--
Sensitive and/or Narrow Therapeutic Index CYP2C8 substrates				
Montelukast	Pioglitazone	Repaglinide ^a	Rosiglitazone	--
Sensitive and/or Narrow Therapeutic Index CYP2C9 substrates				
Celecoxib	Diclophenac	Glimepiride	Tolbutamide	--
Sensitive and/or Narrow Therapeutic Index CYP3A4 substrates				
Alfuzosin	Alprazolam	Atorvastatin ^b	Avanafil	Buspirone
Colchicine	Dihydroergotamine	Eletriptan	Eplerenone	Ergotamine
Felodipine	Lovastatin	Midazolam	Nisoldipine	Tadalafil
Triazolam	Sildenafil	Simvastatin ^b	--	--
Other restricted Medications ^c				
Amlodipine	Benzonatate	Bupropion	Citalopram	Clotrimazole
Cyclobenzaprine	Diazepam	Escitalopram	Fluconazole	Fluoxetine
Guaifenesin	Hydroxyzine	Levothyroxine	Losartan	Meloxicam
Nitrofurantoin	Pravastatin	Sertraline	Tamsulosin	Trazodone
OATP1B1/1B3 substrates				
Atorvastatin ^b	Bosentan	Ezetimibe	Fluvastatin	Glyburide
Pitavastatin	Pravastatin	Repaglinide ^a	Rosuvastatin	Simvastatin ^b
P-gp substrate with Narrow Therapeutic Index				
Apixaban	Dabigatran etexilate		Digoxin	Edoxaban

a. A CYP2C8 and OATP1B1/1B3 substrates.

b. A CYP3A4 and OATP1B1/1B3 substrates.

c. The plasma concentration may decrease due to induction potential of JTE-451 for CYP.

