6.5 Safety Analysis

All safety analyses will be summarized based on the Safety population.

Potentially clinically significant (PCS) abnormalities will be defined according to the Akros Safety Reporting Standards as of 18 Oct, 2004. The PCS values for vital signs, ECG and laboratory data will be flagged in data listings.

Treatment-emergent PCS abnormalities are values that meet the specified criteria after the initiation of study drug (see Section 10.1 for detailed clinically significant criteria).

Treatment-emergent PCS values will be summarized, presenting the number and percentage of subjects who had at least one PCS value on or after the first dose of study drug (JTE-451 or placebo). The denominator is always the number of subjects in the safety population, regardless of whether the subject had any post-baseline measurements. The numerator is the number of subjects in the safety population with any PCS value in the treatment-emergent period. Note that for the purpose of determining PCS abnormalities, baseline is always the last non-missing value before the first dose of study drug. As all procedures will be performed before dosing at each scheduled visit, the values of the scheduled Day 1 collection will be baseline and will not be treatment-emergent PCS.

All safety data will be presented in the data listings, and will be flagged for events of interest (e.g., out of range laboratory data) as appropriate.

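### CPK is measured at all eight visits, but the SAP's only CPK criterion row is an MB-fraction row without a cut-off, so no pre-specified laboratory table counts subjects with a marked rise

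*SAP*

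**What the plan says.** Protocol 3.5.6.14 lists the serum biochemistry analytes, among them "chloride, creatinine phosphokinase, creatinine, gamma-glutamyl transferase". The second item, as printed, is evidently CPK; no fraction is named, and the MB fraction is not listed. Protocol Table 1 and SAP Table 1 both mark serum biochemistry at Visits 1 to 8.

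SAP 10.1 holds the PCS limits. Its heart-function block has rows for AST and LDH, each with a high limit of 3 times the upper limit, and a row "CPK (MB Fraction") in µg/L with a dash for both low and high. There is no other CPK row.

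SAP 6.5 makes PCS depend on those limits: "Treatment-emergent PCS abnormalities are values that meet the specified criteria after the initiation of study drug". SAP 6.5.4 then plans the count: "Number and percentage of subjects with treatment-emergent PCS abnormal values will be summarized by treatment group". It adds Table 3, a categorical table for liver tests.

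Protocol 3.6.1 has a laboratory abnormality recorded as an adverse event when it comes with symptoms, leads to permanent discontinuation of study drug, or requires a change in concomitant therapy. Abnormalities that meet a seriousness criterion are also reported. For the remainder it says: "This does not apply to abnormal vital signs, physical finding or laboratory/ECG results that do not meet the clinical-significance criteria".

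**The concern.** The protocol collects one analyte and the SAP's criteria table names a different one. Followed as written, the plan gathers CPK on every subject at every visit but leaves it out of the table that would show how many subjects in each arm had a marked rise.

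What is at stake is the visibility of an imbalance between either JTE-451 dose and placebo in rises that nobody acted on. Rises of that kind are usually few and large, and a count of subjects above a limit is the natural display. The primary endpoint, the significance level and the sample size are not involved.

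**Working it through.** The plan states no figure here to reproduce. The check is a comparison of the collected analytes with the criteria and the planned tables.

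**Step 1: is CPK collected?** Yes. It is one of 24 analytes in Protocol 3.5.6.14, and the panel is scheduled at 8 of 8 visits.

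**Step 2: which of the 24 have a usable limit in SAP 10.1?**

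- No row for the analyte as collected: CPK, C-reactive protein, globulin (3).
- A row with dashes for both limits: LDL cholesterol, and carbon dioxide if matched to the bicarbonate row (2).
- Usable limit: 24 − 3 − 2 = 19.

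Leaving an enzyme without a limit is therefore the exception. AST, ALT, LDH, ALP and GGT all carry the same limit of at least 3 times the upper limit.

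**Step 3: can a CPK value be PCS?** SAP 6.5 requires a specified criterion. The measured CPK has no row, and the MB row has no limit. The number of CPK values that can qualify is zero, whatever their size.

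**Step 4: does another laboratory table count CPK?** SAP Table 3 covers ALT, AST, total bilirubin and ALP only. SAP 5.3.6 derives a low, normal or high class for each parameter, but SAP 6.5.4 plans no frequency table of that class for biochemistry, and the class does not record how high a value is.

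**Step 5: where would a CPK rise appear?**

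| Kind of rise | AE tables | PCS count by arm | By-visit statistics | Listings |
|---|---|---|---|---|
| With symptoms, permanent discontinuation, changed concomitant therapy, or serious | Yes | No | Yes | Yes |
| None of these | Not required | No | Yes | Yes, with an out-of-range flag as appropriate |

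The by-visit statistics (SAP 6 and 6.5.4) are n, mean, SD, median, minimum and maximum. A maximum shows that at least one subject in an arm had an extreme value at that visit. It does not show whether there was one such subject or several. Nor can the number of subjects with at least one high value over the six post-baseline visits (Visits 3 to 8) be recovered from six separate maxima.

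**The case against.** Several points on the other side have weight.

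- **The AE tables count some rises.** A reader might infer that no table of any kind would count subjects with a CPK rise. That goes too far. SAP 6.5.1 tabulates treatment-emergent events by preferred term, and a rise that led to stopping study drug or changing another medicine is an adverse event under Protocol 3.6.1. Protocol 3.4 also requires prompt evaluation of any CTCAE grade 3 finding. The gap is confined to rises with no symptoms and no action.
- **Extremes would be seen.** The maximum is tabulated by visit and arm, out-of-range values can be flagged in listings, and with about 50 subjects per arm the listings can be read by hand. This stands, but neither output is a count by arm.
- **The plan does not forbid a count.** The footnote to SAP 10.1 lets the criteria be revised, and the mock tables are in a separate document. That makes the fix easy but does not pre-specify it.
- **A count proves little statistically.** Take hypothetical counts of 3 of 50 against 0 of 50. The two-sided Fisher probability is 2 × C(50,3)/C(100,3) = 2 × 19,600/161,700 = 0.24. The SAP plans no tests on laboratory data, and the value of the count is descriptive.
- **Other analytes lack limits too.** C-reactive protein, globulin, LDL cholesterol and carbon dioxide are in the same position. CPK differs in that the table does carry a row for it, but for the wrong fraction.

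A reader might also infer that muscle injury is an expected harm, because Protocol Appendix 1 names seven statins and colchicine under the statement "Use of the following medications are permitted during the study; however, caution should be used when the medications". The documents do not support this. The legible text never names muscle injury, the detailed cautions are redacted, and nothing legible says that JTE-451 raises exposure to these drugs. The one direction stated is a possible decrease, for a group that includes pravastatin. The list is at most a reason for interest in CPK.

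**Conclusion.** The point holds as a minor safety-reporting gap. CPK is collected at 8 of 8 visits, the criteria table has no row for it and no limit in the MB row, and no pre-specified laboratory table counts subjects per arm with a marked rise. Rises that meet the adverse event conditions are covered elsewhere.

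The conclusion rests on two readings. One is that the protocol's entry means CPK as ordinarily reported, without fractionation; that it is total CPK is an inference, since no fraction is named. The other is that the separate mock tables, which are not available here, do not already add a CPK count. The documents give no CPK data, so the number of subjects affected cannot be estimated. The primary analysis is unaffected.

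**What to change.** In SAP 10.1, replace or supplement the MB-fraction row with a row for the CPK actually measured. Give it a high limit as a multiple of ULN, fixed by the sponsor before unblinding. The form already used for AST, ALT, LDH, ALP and GGT, at least 3 times the upper limit, is an available default. Include CPK in the treatment-emergent PCS summary by treatment group under SAP 6.5.4. This would be a reporting threshold only and would not govern how any subject is managed.

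The cost is one table row and one line in a summary that is already planned, with no new data. The downside is that exercise-related rises will be counted too, in all arms.
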